## **Basic Assumption**

It is assumed that:

- The movement applied will be the same for all participants and will be the same for each participant repeatedly.
- All participants will comply with the instructions honestly.
- All participants will have the same psychophysiological condition during the treatment period.

## **Delimitations**

**The principles respected in selecting the cases and data recording are:**

- 1- 40 normal participant will be assigned to group, this number detected by G\*power 3.1 software (Universities, Dusseldorf, Germany) was used for calculation.
- 2- The participant's age ranged from 35 to 45 (**Miranda et al., 2002**).
- 3- The participant from both sex (**Correll et al., 2018**).
- 4- Participant Body mass index (BMI) from (19 to 25) normal weight (**Weisell et al., 2002**).
- 5- Knee flexion and extension ROM will be measured with the digital goniometer.
- 6- Knee flexion and extension ROM will be measured with the rebee wearable sensor.
- 7- The procedures will repeated two times with one week interval between measurements.

## CHAPTER II

# LITERATURE REVIEW

### Range of Motion

Range of motion of the joint is the arc of motion that occurs at a joint, it is one of the factors that determine function of the musculoskeletal system. This parameter should be measured and recorded by a reproducible only method (Yaikwawongs et al., 2009)

The assessment of joint range of motion (ROM) is an important component of a physical therapy examination. These measurements are critical for providing baseline data, determining functional limitations, and monitoring changes in joint mobility in response to treatment. Measurement of ROM may also be used to detect asymmetry and movement restrictions that may increase risk of injury (Clarkson et al., 2005).

Range of motion of the knee joint is one of the major factors determining the outcome after knee injuries. It is also an important measurement required by many knee scoring systems to determine the preoperative status and postoperative outcome (Anouchi et al., 1996).

### Causes of ROM Limitation

Reduced range of movement is where there is a limitation of movement at a joint. Types of reduced range of movements are:

- Muscle Injury
- Ligament injury
- Pain
- Swelling
- Arthritis

(Konor et al., 2012)

[figure not shown]
## Physical Examination of ROM

Each specific joint has a normal range of motion that is expressed in degrees. The reference values for the normal ROM in individuals differ slightly depending on age and gender. For example, as an individual ages, they typically lose a small amount of ROM (Yaikwawongs et al., 2009).

[figure not shown]
Analog and traditional devices to measure range of motion in the joints of the body include the goniometer and inclinometer which use a stationary arm, protractor, fulcrum, and movement arm to measure angle from axis of the joint.

Over the years, the most common instrument used for joint measurement in physio-therapy has been the universal goniometer (UG) (Norkin et al., 1995). Important psychometric characteristics of this instrument, such as intratester and intertester reliability, have been examined in many research studies. In the clinical setting, these characteristics are important because patients are often treated and reassessed, either by the same or by different physical therapists (Gogia et al., 1987).

Many research studies have found the UG to have overall good intratester and intertester reliability. However, the majority of these studies have found intratester reliability to be greater than intertester reliability (Roach et al., 1991)

In addition to the goniometer, another device being used by some clinicians to measure range of motion is the digital inclinometer. The inclinometer is similar to the goniometer in that both are lightweight and portable. However, the inclinometer has significantly more associated cost. The inclinometer has been demonstrated to possess good to excellent reliability and concurrent validity with the universal goniometer (**Clarkson et al., 2005**)

The digital goniometer is the most commonly utilized clinical tool for measuring joint range of motion, it gives the physiotherapist a useful method to diagnose musculoskeletal function in terms of ROM, monitor the progress of an intervention (**Yaikwawongs et al., 2009**).

There is high validity, intra rater and interrater reliability of the digital goniometer (**Svensson et al., 2019**).

To measure joints with the digital goniometer is considered time consuming and difficult with respect to repeated measurements. (**Svensson et al., 2019**), so there is a need to a new device that sensors system could be considered as a clinical measurement for ROM which will reflect in rehabilitation process (**Hamel et al., 2008**).

New evolution for measuring ROM called rebee wearable sensor. With the use of rebee wearable sensor, the ROM of knee joint flexion and extension can be monitored easily, that lead to facilitation of tele rehabilitation. Which the patients are supposed to put on the sensors and perform knee flexion and extension themselves, with or without the supervision from the clinicians.

The patients are supposed to put on the sensors and perform the actions themselves, with or without the supervision from the clinicians/ research. The evolution of sensors technology and applications are easy to use, relatively inexpensive, and highly accessible (**Keogh et al., 2019**)

# CHAPTER III

## SUBJECTS, MATERIALS AND METHODS

This study will be conducted at the Outpatient Clinic of Faculty of Physical Therapy, Pharos University, Alexandria, Egypt. to test the criterion related validity and reliability of rebee wearable sensor in measuring Active Knee Joint ROM compared with digital goniometer measurement.

### **Design of the Study**

The study is Cross Section Study (Observational study).

### **Participants**

40 normal participant will be assigned to one group, this number detected by G\*power 3.1 software (Universities, Dusseldorf, Germany) was used for calculation.

### **Selection of Subjects**

The participant will be recruited from faculty, staff, and students of Pharos University, Egypt. Graduate Program in Physical Therapy after achieving the inclusion and exclusion criteria. Each participant will sign an informed consent before beginning of the study to insure complete satisfaction (Appendix 1)

### **Inclusion Criteria**

1. 40 normal participant's age ranged from 35 to 45. (**Miranda et al., 2002**)
2. The participant from both sex. (**Correll et al., 2018**)
3. Participant Body mass index (BMI) from (19 to 25) normal weight ( $BMI = \text{weight (kg)} / [\text{height (m)}]^2$ ) (**Weisell et al., 2002**).

## Instrumentations

1. Digital goniometer.

The digital goniometer will be used as a valid and reliable ROM measurement tool, the type of digital goniometer will be used in the study called digital absolute axis goniometer with accuracy about 0.99(**Correll et al., 2018**)

2. Rebee wearable sensor and application by XCLR8 Technologies.

The package of sensor and application will be used for measure, interpret and store participant measurement for test the criterion related validity and intrarater reliability of rebee wearable sensor in measuring active knee joint ROM

3. Health weight scale for weight and height measurement to calculate BMI. (BMI= weight (kg) / [height (m)]) (**Weisell et al., 2002**).

## Procedure for testing Validity

The digital goniometer will be used as a valid and reliable ROM measurement tool to be compared with rebee wearable sensor in measuring active knee joint ROM.

## Measure AROM of Knee Flexion with Digital Goniometer

The participant will be at supine position with the testing knee extended, which allows assessment of the joint ROM without interference from tightness in the rectus femoris muscle, axis location at lateral epicondyle of the femur, stationary arm will be along the femur to the greater trochanter, The movement arm will be along the fibula to lateral malleolus.

[figure not shown]
The participant will be asked to flex the testing knee fully through available ROM and the therapist will record the measurement to compare with rebee wearable sensor measurement.

## Measure AROM of Knee Extension with Digital Goniometer

The participant will be at supine position with the testing knee flexed, which allows assessment of the joint ROM without interference from tightness in the rectus femoris muscle, axis location at lateral epicondyle of the femur, stationary arm will be along the femur to the greater trochanter, The movement arm will be along the fibula to lateral malleolus.

The participant will be asked to extend the testing knee fully through available ROM and the therapist will record the measurement to compare with rebebe wearable sensor measurement.

The following picture illustrates that measurement with the digital goniometer will be from the similar supine position of measurement with the conventional goniometer.

## Procedure for testing Reliability

Designed according to Guidelines for reporting Reliability and Studies, investigating the intrarater reliability of a rebebe wearable sensor will be conducted. The study will be designed in accordance with the ethical guidelines from the Helsinki declaration of ethical principles (World Medical Association (Kottner et al., 2011)).

Written consent will be retrieved from all subjects before participating in the study, the procedures will be repeated two times with one week interval between measurements. Researcher will record all the measurement.

### **Knee Active ROM Measurement with Rebee Wearable Sensor**

This process postulated by Kimberlin, 2008

[figure not shown]
To detect the joints ROM, the sensors were placed in the most distal part of the limbs with prominent bony landmarks at the level of lateral malleolus. It will be stabilized on the testing limbs by elastic bands. With the sensor light facing Lateral malleolus

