### **Measure AROM of Knee Flexion with Rebee Wearable Sensor**

The participant will be standing in upright position, the sensor position at the level of the Lateral malleolus, participant will be asked to flex the testing knee fully while standing supported in one leg.

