### **Measure AROM of Knee Extension with Rebee Wearable Sensor**

The participant will be sitting at the edge of plinth with knee flexed, the sensor position at the level of the Lateral malleolus, participant will be asked to extend the testing knee through the full ROM.

[figure not shown]

The Digital goniometer and rebee wearable sensor will be used for comparison of their validity for measuring knee joint flexion and extension ROM.

Rebee wearable sensor will be used as mentioned above and this procedures will repeated two times with one week interval between measurements to test its reliability. Researcher will records all the measurement.

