### **Steps for Using Rebee Sensor Package**

- 1- Take the charging end of the charging cable and look for the charging port on the sensor.

[figure not shown]
2- Making sure the cable aligns with the port then connect the charger.

[figure not shown]
- 3- The USB end of the charging cable must be connected to a USB port / USB charger.
- 4- Check the sensor for a red LED light to know that it is successfully charging. The red LED will turn off once the device is fully charged.

5- Wearing the devise at the level of the Lateral malleolus with the sensor light facing Lateral malleolus.

[figure not shown]
6- Connecting the sensor to the device

[figure not shown]
Step a: Switch on the sensor device.

Step b: Go to phone's settings and turn on device's Bluetooth.

7- Look for “HC-06” (Default sensor name) under “Available devices” and tap on it.

8- Identifying the Sensors to Software

Step a: Connect the sensor you are trying to identify  
 Step b: Look for the sensor in the list with the name “HC-06”

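### As written, the only sensor is on the lower leg while the goniometer reads the thigh-to-shank angle, and the text sets no common zero, start angle or thigh control beyond gross posture

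*Combined protocol and SAP*

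**What the plan says.** **Goniometer.** Under Measure AROM of Knee Flexion with Digital Goniometer, the axis is at the lateral femoral epicondyle, the "stationary arm will be along the femur to the greater trochanter", and the moving arm follows the fibula. The extension section repeats this. The reading is therefore an angle between two body segments. Both goniometer tests are supine. Flexion starts with the knee extended. For extension: "The participant will be at supine position with the testing knee flexed". No angle is given.

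**Sensor.** Under Knee Active ROM Measurement with Rebee Wearable Sensor, "the sensors were placed in the most distal part of the limbs with prominent bony landmarks at the level of lateral malleolus". On fixation: "It will be stabilized on the testing limbs by elastic bands". For flexion, the "participant will be asked to flex the testing knee fully while standing supported in one leg". For extension: "The participant will be sitting at the edge of plinth with knee flexed, the sensor position at the level of the Lateral malleolus". Again no start angle is given.

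**Set-up.** Steps for Using Rebee Sensor Package covers charging, "Wearing the devise at the level of the Lateral malleolus with the sensor light facing Lateral malleolus", pairing by Bluetooth and identifying the sensor in the software. The text contains no zeroing or calibration step.

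**Not stated in the text.** How the app turns its signal into a knee angle, and whether the recorded value for either device is an end position or an arc.

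**Analysis.** Statistical Analysis names means, SDs and Pearson's r.

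**The concern.** The study asks whether the sensor agrees with the goniometer and whether it repeats after one week. Both questions presuppose that the two devices measure the same angle. A device on the lower leg senses the orientation of the lower leg. That orientation equals the knee angle only if the thigh is fixed or separately measured and the zero is known. The written procedure secures neither.

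Hip movement during one-legged standing, or a different starting bend of the knee, could therefore be counted as sensor invalidity or unreliability. The data would give no way to separate these from true device error.

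**Working it through.** The documents give no figure for sensor error, thigh movement or spread of knee angles, so there is no plan figure to reproduce. Every angle and SD below is an assumption.

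**1. Geometry (sagittal plane).** Let K be the thigh-to-shank angle and h the forward inclination of the thigh.
- Goniometer reading = K.
- Tilt of a sensor on the shank alone = K − h.
- With K = 135 degrees, h = 0, 5 and 10 give sensor readings of 135, 130 and 125. A thigh extended by 10 degrees (h = −10) gives 145.

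**2. Start angle.** If the app reports an arc, reading = start angle − end angle, plus any thigh movement. Seated extension to 0 from a start of 80, 90 or 100 degrees gives 80, 90 or 100. A 5-degree thigh lift at the end adds 5. If the app reports absolute tilt, the start angle drops out, but thigh angle and the choice of zero remain.

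**3. Effect on reliability and agreement.** Assume a between-person SD of 6 (variance 36), an error SD of 2 for each device (variance 4), and thigh variation with SD s that is independent of K and random between trials.
- One-week ICC of the sensor = 36 / (36 + 4 + s²)
- Half-width of the 95% limits of agreement = 1.96 × √(4 + 4 + s²)

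| s (degrees) | ICC | Limits of agreement (degrees) |
|---|---|---|
| 0 | 36/40 = 0.90 | 1.96 × √8 = ±5.5 |
| 2 | 36/44 = 0.82 | 1.96 × √12 = ±6.8 |
| 5 | 36/65 = 0.55 | 1.96 × √33 = ±11.3 |

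**4. The planned statistic.** With equal variances in the two weeks, the expected week-to-week Pearson r equals the ICC above. Between devices, r = 36 / √(40 × (40 + s²)):
- s = 0: 36/40 = 0.90
- s = 2: 36/√1760 = 0.86
- s = 5: 36/√2600 = 0.71

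**5. If thigh posture is a stable personal habit.** The thigh variance then moves into the between-person part. At s = 5, the sensor's ICC is (36 + 25)/(36 + 25 + 4) = 61/65 = 0.94, while the limits of agreement stay at ±11.3. Reliability would look good although agreement is as poor as before.

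**6. With the thigh still and a common zero,** h = 0 and the geometric term vanishes. Only the devices' own errors remain.

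**The case against.** **Device workings are undescribed.** A reader might infer that thigh movement and start angle certainly enter degree for degree. The documents do not support that. The app's method is not given, the general placement section speaks of sensors in the plural, and the set-up figures are not in the text available for review. A figure might show a thigh sensor or a zeroing step. The absence can be claimed for the text only, and the one-for-one effect is conditional.

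**Posture is partly controlled.** Upright standing gives a roughly vertical thigh and an extended knee at the start, and sitting on a plinth supports the thigh. Basic Assumption also takes the movement to be the same across participants and repetitions. This limits the likely size of the effect. It is still gross posture and an assumption, and neither holds the thigh through a full active movement.

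**Start angle may not matter.** If both devices record the end angle at full extension, the flexed start is irrelevant. That is correct, but the plan does not say that they do. The same gap applies to the goniometer.

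**A hidden extension offset.** A reader might infer that an arc near 90 degrees set against an end angle near 0 would pass unnoticed with r unchanged. It would not. The planned means would show it. With a constant start, arc = start − end, so r would change sign. With varying starts, r would be attenuated.

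**Thigh movement belongs to real use.** The device is intended for patients with or without supervision, so error from thigh movement may be a genuine limitation. That stands as a limit on what a stabilised study can conclude. Without control or a record of thigh position, however, the study cannot tell this limitation from device error.

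**The SDs are assumed, and ICC and limits of agreement are not planned.** Both points stand. The numbers are illustrative only.

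**Conclusion.** The concern holds in conditional form. As the text describes it, the only sensor is at the malleolus and the goniometer reads a two-segment angle. The text sets no common zero, no extension start angle, no recorded quantity, and no thigh control beyond gross posture. If the app has no thigh reference, thigh movement enters one for one. If it reports an arc, the start angle enters too.

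On the assumed SDs, the effect ranges from modest at a thigh SD of 2 degrees to severe at 5 degrees, where more than a third of the ICC is lost and the limits of agreement are about twice as wide. The ICC loss requires thigh variation that is random between trials. Stable personal posture would leave the ICC high and harm agreement only.

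The documents do not establish that the sensor is invalid, that the app ignores the thigh, or that a gross offset would escape the planned analysis. The gap is worth closing before data collection because the change is cheap and determines what is being measured.

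**What to change.** Amend the two goniometer sections and the three sensor measurement sections of Chapter III:

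1. Record the same quantity with both devices: either the end angle with full extension as 0, or an arc from the same recorded start angle. Use the same defined start position for each movement. If an end angle is chosen for extension, record the start angle as well, so that a reading referenced to a flexed start can be converted.
2. Reference the sensor to that start position before each trial. If the app cannot be zeroed, record its start reading and subtract it.
3. Keep the thigh against a fixed support in standing and flat on the plinth in sitting. Repeat any trial with visible thigh movement, under a rule set in advance that applies equally to both devices.
4. State how the app derives the knee angle and whether a sensor is worn on the thigh. If the app does correct for the thigh, say how.

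The cost is procedural wording and perhaps a minute per trial (an estimate, since the documents give no timing), with no new device or staff. The downside is that the conclusion is then limited to stabilised, supervised measurement and does not extend to unsupervised home use. The report should say so.

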### **Measure AROM of Knee Flexion with Rebee Wearable Sensor**

The participant will be standing in upright position, the sensor position at the level of the Lateral malleolus, participant will be asked to flex the testing knee fully while standing supported in one leg.

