## **Statistical Analysis**

Statistical methods will be used to calculate the reliability and validity of our measurements will be descriptive statistics for mean and standard deviation, also the Pearson product-moment correlation coefficient (r), an assessment of covariance.

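### The goniometer is read supine and the sensor standing or sitting, so the validity comparison cannot separate the device from the posture

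*Combined protocol and SAP*

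**What the plan says.** Chapter III describes four measurement procedures.

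- Goniometer, flexion: "The participant will be at supine position with the testing knee extended".
- Goniometer, extension: "The participant will be at supine position with the testing knee flexed".
- Sensor, flexion: "The participant will be standing in upright position, the sensor position at the level of the Lateral malleolus"; the participant then bends the tested knee fully while supported on the other leg.
- Sensor, extension: "The participant will be sitting at the edge of plinth with knee flexed".

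Both goniometer sections say the reading is recorded for comparison with the sensor. The sensor extension section closes the loop: "The Digital goniometer and rebee wearable sensor will be used for comparison of their validity for measuring knee joint flexion and extension ROM".

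The only statement about matching positions is in the goniometer extension section: "measurement with the digital goniometer will be from the similar supine position of measurement with the conventional goniometer". It relates two kinds of goniometer and does not mention the sensor.

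The Statistical Analysis section plans means, standard deviations and the "Pearson product-moment correlation coefficient (r), an assessment of covariance". It sets no threshold for r and names no paired difference, limits of agreement or posture term.

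**The concern.** A criterion-validity study asks whether a new device gives the same answer as the reference when both measure the same thing. Here each device has its own posture for each movement, so the two readings come from two different tests of the knee. If they disagree, the sensor or the posture may be responsible. If they correlate well, the result shows a linear association between two tests, not that the devices report the same angle.

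The protocol itself implies that posture matters. Both goniometer sections justify the supine position as avoiding interference from rectus femoris tightness, and the sensor sections give no such assurance for standing or sitting. Tightness plausibly differs between people, and a posture effect that differs between people is the kind that lowers r.

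Criterion validity is one of the two stated purposes of the study. No later analysis can recover same-posture readings that were never taken.

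**Working it through.** **Step 1: which device is read in which posture.**

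| Movement | Goniometer | Sensor |
|---|---|---|
| Flexion | supine | standing on one supported leg |
| Extension | supine | sitting at plinth edge |

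No section describes a goniometer reading in standing or sitting, a sensor reading in supine, or both devices on one repetition. The one-week repeat does not help, whether it covers both devices (Delimitations; Procedure for testing Reliability) or is read as covering only the sensor (sensor extension section), because it repeats each device in its own posture. The Basic Assumption section assumes the same movement across participants and repetitions, which does not override written postures that differ by device. The confounding follows from the design and needs no numbers.

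**Step 2: can the planned statistics tell the explanations apart?** The plan's only related figure is a sample size of 40 from G\*Power, stated without inputs. It cannot be reproduced, and this point does not depend on it. The documents give no SDs, so these are assumptions for illustration: between-person SD 7 degrees (variance 49), error SD 2 per device (variance 4), and an extra stable person-level component of SD p that is uncorrelated with the participant's range of motion (ROM).

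- Case A: the sensor is accurate, and p is a posture effect that varies between people.
- Case B: posture has no effect, and p is a person-specific sensor error.

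As planned, both cases have

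- validity r = 49 / √(53 × (53 + p²))
- sensor retest r = (49 + p²) / (53 + p²)

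With both devices read in the sensor's posture, A has r = (49 + p²) / (53 + p²), and B keeps r = 49 / √(53 × (53 + p²)).

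| p | Validity r as planned, A and B | Sensor retest r, A and B | Same posture, A | Same posture, B |
|---|---|---|---|---|
| 0 | 0.925 | 0.925 | 0.925 | 0.925 |
| 3 | 0.855 | 0.935 | 0.935 | 0.855 |
| 5 | 0.762 | 0.949 | 0.949 | 0.762 |
| 7 | 0.666 | 0.961 | 0.961 | 0.666 |

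For p = 5, for example, 49/√(53 × 78) = 0.762 and 74/78 = 0.949. As planned, A and B coincide in every row. In a common posture they separate.

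**Step 3: other inputs.** Let k be the ratio of the posture-effect SD to the between-person SD, and e the ratio of error variance to true variance. Then r = 1/√((1 + e)(1 + k² + e)). For k = 0.25, 0.5, 0.75 and 1.0, error-free devices (e = 0) give 0.97, 0.89, 0.80 and 0.71. Devices with reliability 0.95 (e = 1/0.95 − 1) give 0.92, 0.85, 0.77 and 0.68, against 0.95 with no posture effect. A perfect sensor can therefore show a clearly reduced r.

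**Step 4: a posture shift common to everyone.** This leaves r unchanged and goes entirely into the means. With an assumed ROM SD of 6 and error SD of 1.5, r = 36/(36 + 2.25) = 0.94 whether the shift is 0, 5 or 10 degrees, while the means differ by the full shift.

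**Step 5: precision at n = 40.** For r = 0.762, the Fisher z interval is tanh(atanh(0.762) ± 1.96/√37) = 0.59 to 0.87. If r were tested against zero at two-sided 5% (not stated in the plan), the critical value would be 0.31, so every expected r above exceeds it. If limits of agreement were added, their half-width would be 1.96 × √(8 + p²) = 5.5, 8.1, 11.3 and 14.8 degrees for p = 0, 3, 5 and 7, the same in A and B.

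**The case against.** The mismatch may be deliberate. The Significance of the Study section notes a preference among some researchers for measuring lower-limb range in functional positions such as standing, and the goniometer sections give a reason for supine. Comparing the sensor as used with a supine reference would then be a choice. This explains the design but does not remove the confounding. If functional positions are the target, the reference can be read there too.

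Several narrower objections stand:

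- All magnitudes are assumed, and one set of SDs serves both movements. They show that the two explanations cannot be separated, not how large the posture effect is.
- Person-specific posture variation lowers r, so by itself it works against a validity claim. Over-claiming would come mainly from the missing threshold for r and the missing agreement statistic, a separate weakness that matching postures would not cure.
- No formal comparison of means is planned, so that part of the concern applies to the reported means or to an agreement analysis added later.
- The text gives the extension start only as a flexed knee, without an angle, for both devices. The figures cannot be seen here, and it is not stated whether the devices report an end angle or an excursion. This is a secondary point.

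None of these supplies a reading in which device and posture can be told apart.

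**Conclusion.** The concern holds and should be fixed before data collection. As written, neither a favourable nor an unfavourable correlation answers the validity question in hypotheses 1 and 2. The confounding rests on the text alone. Its possible size (r falling from 0.925 to between 0.855 and 0.666) rests on assumed SDs and on a posture effect that is stable and unrelated to the participant's ROM. Hypotheses 3 and 4 are not affected, because the sensor is repeated in its own posture.

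**What to change.** Amend the four measurement sections so that, for each movement, both devices are read in the same position from the same stated start position. One way is to take the goniometer reading in the sensor's positions: supported one-leg standing for flexion and sitting at the plinth edge for extension. Read both devices on the same repetition where the strap allows. Otherwise use consecutive repetitions in the same session, with device order alternated across participants. The supine goniometer reading can stay as a secondary description, and keeping it beside the matched reading would let device and posture be separated.

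If the postures are not changed, report r as the correlation between two different tests and not as validity of the sensor.

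The cost is protocol wording and rater practice, with the same devices, participants and visits. There are three downsides. Aligning a goniometer in standing is less convenient. The strap may partly cover a landmark the goniometer needs, since "the sensors were placed in the most distal part of the limbs with prominent bony landmarks at the level of lateral malleolus". Values will also be less comparable with supine reference values.
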